Statistical significance testing will be one-sided as described in Section 7.4.4.1, and performed using $\alpha=0.10$. P-values will be reported for all statistical tests, rounded to four decimal places. P-values less than 0.0001 will be displayed as “<0.0001”; p-values greater than 0.9999 will be displayed as “>0.9999”. Tests of interaction terms, if applicable, will be two-sided and performed using $\alpha=0.10$.

7.1.2 *Standard Calculations*

Where appropriate, the calculated study day of each assessment or event will be presented with the assessment or event date on subject data listings, where study day will be determined as:

- The assessment/event date minus the date of first dose, if the assessment/event date is prior to the date of first dose; and
- The assessment/event date minus the date of first dose, plus one, if the assessment/event date is on or after the date of first dose.

Other variables requiring calculations will be derived using the following formulas:

- **Days:** A duration between two dates expressed in days will be calculated using the following conventions:
 - Later date – earlier date + 1, if the earlier date is on or after the date of first dose of study drug; or
 - Later date – earlier date, if the earlier date is prior to the date of first dose of study drug.
- **Change from Baseline:** Change from baseline will be calculated as the post-baseline value minus the baseline value;
- **Percentage Change from Baseline:** Percentage change from baseline will be calculated as the change from baseline divided by the baseline value, multiplied by 100.
- **Rank Transformation:** All raw data will be ranked together within time point without regard to treatment group, from smallest value to highest value. The smallest observation will be assigned the rank of 1, the second smallest the rank of 2, and so on. Average ranks will be used for tied observations.

Unless otherwise noted, values reported as greater than or less than some quantifiable limit (e.g., “< 1.0”) will be summarized with the sign suppressed in summary tables and figures, using the numeric value reported. Data will display on subject listings to include the sign.

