The primary efficacy endpoint is the change from baseline to the end of therapy in the mean HDSM-Ax score. The primary efficacy endpoint will be analyzed both as a continuous measure and as a binary outcome. As a continuous measure, the HDSM-Ax change scores will be compared between treatment groups in pairwise fashion by an ANCOVA model adjusting for the baseline HDSM-Ax score. The analysis will be performed with no imputation of missing data. As a binary measure, i.e. achieving a ≥ 1 -point improvement or not from baseline to end of therapy, a binary logistic regression will be performed with treatment assignment and baseline HDSM-Ax score as independent variables in the model. Any subject without a definable 1-point improvement (e.g., missing data) between Baseline and End of Treatment will be considered a non-responder. P values will generally be regarded as descriptive and statistical significance will be assessed using a gate-keeping hierarchy as described in Section [7.4.6.5](#) for both the continuous measure and binary data analyses.

The null hypothesis to be tested for the continuous measure is as below:

$$H_0: \mu_A \geq \mu_P;$$

where μ_A and μ_P represent the true underlying mean change scores for Treatment A (active drug) and Treatment P (vehicle), respectively. The alternate hypothesis to be tested is that the true active treatment group mean change score is smaller than the true vehicle group mean change score:

$$H_1: \mu_A < \mu_P;$$

Tested in the logit scale, the null hypothesis for the dichotomous outcome is that the true proportion of subjects with a 1 point or more improvement is lower in the active treatment group:

$$H_0: P_A \leq P_P;$$

The alternate hypothesis to be tested is that the true proportion of subjects with a 1 point or more improvement is higher in the active treatment group:

$$H_1: P_A > P_P;$$

7.4.4.2 *Sensitivity Analysis by Mixed Effects Models*

As a method that is known to be robust to missing data, mixed model repeated measures (MMRM) analyses will also be performed for the primary efficacy endpoint using all available HDSM-Ax change from baseline data on study days 8, 15, 22, 29, 36, and end of therapy. As fixed effects, treatment (active treatment group or vehicle gel), baseline HDSM-Ax score and visit (included in the class statement as a class variable) and baseline*visit interactions will be

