included in the model both without and with treatment*visit interaction terms. Subject will be analyzed as a random effect. Similarly, MMRMs will also be performed for the primary efficacy endpoint using HDSM-Ax dichotomized response data, and HDSM-Ax + GSP dichotomized response data. The models will be the same as the model for continuous data but the dependent variable of interest will be the response status with a logit link, using the SAS Proc GLIMMIX module. Both the heterogeneous CS (CSH) and TOEP (TOEPH) covariance structures will be considered and the structure with lower AIC will be used. The percentage of responders will also be summarized at each visit in the result table.

MMRM analysis as described above will also be performed for continuous GSP data (both Normal model and using rank transformed data) and binary GSP response (i.e. 50% reduction from baseline) data.

7.4.4.3 *Additional Sensitivity Analysis*

An additional sensitivity analysis will be performed as follows. For subjects missing all 3 end of therapy values, the data will be imputed by the last three available post-baseline (i.e., from Day 8 onward) assessment values. This analysis will be performed for both the continuous data analysis and the binary data analysis using the same ANCOVA models as described above.

7.4.5 *Secondary and Other Efficacy Endpoint Analysis Methods*

Baseline and End of Therapy values for HDSS and GSP are defined as follows.

HDSS:

- Baseline value = average of two screening values, i.e., Visit 1 and Visit 4
- End of Therapy value = average of Days 41, 42, and 43 measurements, i.e., Visit 11, Visit 12, and Visit 13, respectively.
- End of Therapy Imputed value = includes subjects missing all end of therapy values, where data is imputed by the last three available post-baseline visits.

Gravimetric Sweat Production (both axilla combined total):

- Baseline value = the median of GSP1, GSP2, and GSP3 measurements obtained on Visit 2, Visit 3, and Visit 4, respectively. The mean value of the same visits will also be used for analysis.
- End of Therapy value = the median of GSP4, GSP5, and GSP6 measurements obtained on Visit 11, Visit 12, and Visit 13, respectively. The mean value of the same visits will also be used for analysis.

- End of Therapy Imputed value = includes subjects missing all end of therapy values, where data is imputed by the last three available post-baseline visits.

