^[4] P-values comparing active dose to vehicle are based on an ANCOVA model with covariate adjustment for the baseline value.

Reference: Listing #(s)

Path\filename.sas dddmmYYYY hh:mm

Programming Notes: Continue for End of Therapy Imputed^[3], and BBI -4000 Doses (10%, 15%). Repeat for Table 14.2.1.4 HDSM-Ax End of Therapy Change from Baseline ANCOVA (PP Population)

Table 14.2.1.5
HDSM-Ax Change from Baseline MMRM and Change from Baseline by Visit ANCOVA
mITT Population

Time Point	Vehicle (N=)			BBI-4000 5% (N=)		
	Observed Value	Change from Baseline	% Change from Baseline	Observed Value	Change from Baseline	% Change from Baseline
Baseline ^[1]						
n	n			n		
Mean (SD)	x.x (x.xx)			x.x (x.xx)		
Median	x.x			x.x		
Min, Max	x.x, x.x			x.x, x.x		
Day 8						
....						
LSM (SE)	xx.x (xx.xx)	xx.x (xx.xx)	xx.x (xx.xx)	xx.x (xx.xx)	xx.x (xx.xx)	xx.x (xx.xx)
LSMD (active dose – vehicle) (SE)		xx.x (xx.xx)	xx.x (xx.xx)		xx.x (xx.xx)	xx.x (xx.xx)
95% CI of LSMD		xx.x, xx.x	xx.x, xx.x		xx.x, xx.x	xx.x, xx.x
ANCOVA p-value ^[2]					x.xxxx	x.xxxx
....						
MMRM treatment p-value ^[3]					x.xxxx	x.xxxx
MMRM treatment*visit p-value ^[4]					x.xxxx	x.xxxx

Abbreviations: ANCOVA, analysis of covariance; HDSM-Ax, Hyperhidrosis Disease Severity Measure-Axillary; mITT, Intent-to-Treat; MMRM, mixed model for repeated measures; LSM, Least Square Mean; LSMD Least Square Mean Difference

^[1] Baseline is defined as the average of any available Visit 1 (Screening) and Visit 4 (Rescreening) values.

^[2] P-values comparing active dose to vehicle are based on an ANCOVA model with covariate adjustment for the baseline value.

^[3] P-value comparing active dose to vehicle are based on an MMRM with subject as a random effect, treatment, protocol-specified visit, baseline, and baseline*visit interaction as fixed effects.

^[4] P-value is for the collective treatment*visit interaction based on an MMRM with subject as a random effect, and treatment, protocol-specified visit, treatment*visit interaction, baseline, and baseline*visit interactions as fixed effects.

Reference: Listing #(s)

Path\filename.sas dmmmyyyy hh:mm

Programming Notes: Table continues on next page.

- *Continue for Day 8 summary statistics (n, Mean (SD), Median, and Min, Max).*
- *Continue for Days 15, 22, 29, 36, and 57, each visit to include summary statistics.*
- *Continue for remaining BBI -4000 Doses (10%, 15%).*
- *For Days 8, 15, 22, 29, 36, 41-43, and 57 include ANCOVA p-value for each visit.*

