- *For MMRM analyses, use data on Days 8, 15, 22, 29, 36 and End of Therapy.*
- *MMRM p-values are not associated with any visit Day. Show treatment and treatment*visit p-values once at bottom of each treatment group.*
- *Repeat for Table 14.2.1..6 HDSM-Ax Change from Baseline MMRM and Change from Baseline by Visit ANCOVA (PP Population)*

Table 14.2.1.7
HDSM-Ax Responder MMRM
mITT Population

HDSM-Ax Parameter	Time Point	Vehicle	BBI-4000 5%	
		(N=)	(N=)	P-value ^[1]
Reduction from Baseline ^[2] ≥1	Day 8	n (x.x%)	n (x.x%)	x.xxxx
	Day 15	n (x.x%)	n (x.x%)	x.xxxx
	Day 22	n (x.x%)	n (x.x%)	x.xxxx
	Day 29	n (x.x%)	n (x.x%)	x.xxxx
	Day 36	n (x.x%)	n (x.x%)	x.xxxx
			
	End of Therapy ^[3]	n (x.x%)	n (x.x%)	x.xxxx
	MMRM treatment p-value ^[4]			x.xxxx
	MMRM treatment*visit p-value ^[5]			x.xxxx
Reduction from Baseline ^[2] ≥2	...			

Abbreviations: HDSM-Ax, Hyperhidrosis Disease Severity Measure-Axillary; mITT, Intent-to-Treat; MMRM, mixed model for repeated measures

Note: Responder is defined as a subject who achieved the reduction in HDSM-Ax score specified in the HDSM-Ax Parameter column, between Baseline and End of Therapy. Subjects without a defined improvement in score are considered non-responders.

^[1] P-values comparing active treatment to vehicle are based on a binary logistic regression model where treatment and baseline HDSM-Ax Score are predictors.

^[2] Baseline is defined as the average of any available Visit 1 (Screening) and Visit 4 (Rescreening) values.

^[3] End of Therapy is defined as the average of any available Day 41, Day 42, and Day 43 values.

^[4] P-values comparing active dose to vehicle are based on an MMRM with subject as a random effect, treatment, protocol-specified visit, baseline, and baseline*visit interaction as fixed effects.

^[5] P-value is for the collective treatment*visit interactions based on an MMRM with subject as a random effect, and treatment, protocol-specified visit, treatment*visit interaction, baseline, and baseline*visit interactions as fixed effects.

Reference: Listing #(s)

Path\filename.sas ddmmmyyy hh:mm

Programming Notes: Continue for Days 41, 42, 43, 57, HDSM-Ax ≥2, and remaining BBI-4000 dose groups (10%, 15%). Repeat as Table 14.2.1.8 HDSM-Ax Responder MMRM (PP Population). MMRM = generalized linear mixed model for repeated measures, with logit linkage. For MMRM analyses, use data on Days 8, 15, 22, 29, 36 and End of Therapy.

Table 14.2.2.1
HDSM-Ax and GSP Responder MMRM
mITT Population

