		Observed Value	Change from Baseline	% Change from Baseline	Observed Value	Change from Baseline	% Change from Baseline
Baseline ^[2]	Median						
n		n			n		
Mean (SD)		x.x (x.xx)			x.x (x.xx)		
Median		x.x			x.x		
Min, Max		x.x, x.x			x.x, x.x		
Day 8							
....							
LSM (SE)		xx.x (xx.xx)	xx.x (xx.xx)	xx.x (xx.xx)	xx.x (xx.xx)	xx.x (xx.xx)	xx.x (xx.xx)
LSMD (active dose – vehicle) (SE)			xx.x (xx.xx)	xx.x (xx.xx)		xx.x (xx.xx)	xx.x (xx.xx)
95% CI of LSMD			xx.x, xx.x	xx.x, xx.x		xx.x, xx.x	xx.x, xx.x
ANCOVA p-value ^[3]						x.xxxx	x.xxxx
....							
MMRM treatment p-value ^[4]						x.xxxx	x.xxxx
MMRM treatment*visit p-value ^[5]						x.xxxx	x.xxxx

Abbreviations: ANCOVA, analysis of covariance; GSP, gravimetrically measured sweat production; mITT, Intent-to-Treat; MMRM, mixed model for repeated measures; LSM, Least Square Mean; LSMD Least Square Mean Difference

^[1] Method of calculating average for Baseline and End of Therapy.

^[2] Baseline is defined as the median/mean of any available Visit 2, Visit 3, and Visit 4 values.

^[3] P-values comparing active dose to vehicle are based on an ANCOVA model with covariate adjustment for the baseline value.

^[4] P-value comparing active dose to vehicle are based on an MMRM with subject as a random effect, treatment, protocol-specified visit, baseline, and baseline*visit interaction as fixed effects.

^[5] P-value is for the collective treatment*visit interactions based on an MMRM with subject as a random effect, and treatment, protocol-specified visit, treatment*visit interaction, baseline, and baseline*visit interactions as fixed effects.

Reference: Listing #(s)

Path/filename.sas ddmmmyyyy hh:mm

Programming Notes: Table continues on next page.

- Continue for Day 8 summary statistics (n, Mean (SD), Median, and Min, Max).
- Continue for Days 15, 22, 29, 36, and 57, each visit to include summary statistics.
- Continue for remaining BBI -4000 Doses (10%, 15%).
- For Days 8, 15, 22, 29, 36, 41-43, and 57 include ANCOVA p-value for each visit.
- For MMRM analyses, use data on Days 8, 15, 22, 29, 36 and End of Therapy.
- MMRM p-values are not associated with any visit Day. Show treatment and treatment*visit p-values once at bottom of page for each treatment group.
- Repeat analyses with mean method for calculating Baseline and EoT.
- Repeat for Table 14.2.3.10 GSP Change from Baseline MMRM and Change from Baseline by Visit ANCOVA (PP Population)

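### The MMRM planned as the missing-data check on the continuous primary endpoint reports no end-of-therapy treatment difference

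*SAP*

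**What the plan says.** The continuous primary endpoint is HDSM-Ax change to end of therapy, the mean of whichever Day 41, 42 and 43 values are available. It is analysed by ANCOVA adjusted for baseline, without imputation (SAP 7.4.4.1; Table 14.2.1.3 footnotes).

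SAP 7.4.4.2 then adds the sensitivity analysis: "As a method that is known to be robust to missing data, mixed model repeated measures (MMRM) analyses will also be performed". It uses Days 8, 15, 22, 29, 36 and end of therapy. The fixed effects are "included in the model both without and with treatment*visit interaction terms". The section names no contrast, estimate or interval at end of therapy.

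The output is set by the shell for Table 14.2.1.5, repeated for the PP population as 14.2.1.6:

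- Footnote 3: "P-value comparing active dose to vehicle are based on an MMRM with subject as a random effect, treatment, protocol-specified visit, baseline, and baseline*visit interaction". This is the model without treatment-by-visit.
- Footnote 4: "P-value is for the collective treatment*visit interaction based on an MMRM with subject as a random effect".
- Programming notes: "MMRM p-values are not associated with any visit Day". By-visit p-values come from a different model: "For Days 8, 15, 22, 29, 36, 41-43, and 57 include ANCOVA p-value for each visit".

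The LS-mean and LS-mean-difference rows carry no model label. They sit directly above the ANCOVA p-value and match the rows of the ANCOVA-only Table 14.2.1.3. The continuous GSP shell, Table 14.2.3.9, has the same layout: "Show treatment and treatment*visit p-values once at bottom of page for each treatment group". No other table listed in Appendix A gives an MMRM end-of-therapy contrast for continuous HDSM-Ax.

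**The concern.** A missing-data sensitivity analysis should keep the target of the primary analysis and change only the assumption about the missing values. This one changes both. Without treatment-by-visit, the model has a single treatment effect common to all six occasions, so its p-value tests a weighted average of the visit effects. The collective interaction p-value asks whether the effect varies over visits. It says nothing about the size of the effect at end of therapy, and the SAP does not say what follows if it is significant.

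If the MMRM and the ANCOVA agree or disagree, the reader cannot tell whether missing data or the different target is responsible. Of the planned continuous end-of-therapy checks, the MMRM is the only one that could use dropouts' earlier visits without carrying those values forward. Its relevant result is the one left out.

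**Working it through.** **The plan's own figure.** SAP 7.6 assumes a difference of 0.18, SD 0.36, 50 per arm and one-sided 0.10. SE = 0.36 × √(2/50) = 0.072. Power = Φ(0.18/0.072 − 1.282) = Φ(1.218) = 0.888, against a stated 0.89. It reproduces, and it refers to the end-of-therapy difference.

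**Assumptions.** The documents give no HDSM-Ax time course and no between-visit correlation. I use three effect profiles, as fractions of 0.18 over the six occasions:

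- constant: 1 throughout
- building: 0.2, 0.4, 0.6, 0.8, 0.9, 1
- lost at end of therapy: 1, 1, 1, 1, 1, 0

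The central correlation is 0.5, with 0.3 and 0.7 as a range. No baseline covariate is used, and the covariance is taken as known.

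**What the no-interaction model estimates.** The pooled effect is w′d, with w proportional to S⁻¹1, where S is the covariance over the six occasions. For the building profile:

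| Covariance | Weights | Fraction of end-of-therapy effect | Pooled effect |
|---|---|---|---|
| Exchangeable, equal variances | 1/6 each | 3.9/6 = 0.650 | 0.117 |
| End of therapy as a three-day mean | (1,1,1,1,1,3)/8 | 5.9/8 = 0.738 | 0.133 |
| CSH, correlation 0.3, SD rising 25% | early visits heavier | 0.553 | 0.100 |
| CSH, correlation 0.5, SD rising 25% | early visits heavier still | 0.483 | 0.087 |

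With a constant effect the fraction is 1.000 and there is no mismatch.

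**Does the interaction p-value protect the reader?** SAP 7.1.1 sets its level: "Tests of interaction terms, if applicable, will be two-sided and performed using" 0.10. Per dose it is a 5-df test. Under the exchangeable structure its noncentrality is (n/2) × Σ(dₖ − d̄)² / [σ²(1 − ρ)]. At ρ = 0.5 and n = 50:

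- Building: 25 × (0.475 × 0.0324)/(0.1296 × 0.5) = 5.94, giving power 0.557.
- Lost: 25 × (0.8333 × 0.0324)/0.0648 = 10.42, giving power 0.799.

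Across the equal-variance and three-day-mean structures at 50 to 55 per arm, the test flags the building profile in 53–60% of trials and the lost profile in 80–95%. At ρ = 0.3 the ranges are 34–47% and 65–77%. At ρ = 0.7 they are 78–86% and 96–100%.

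The pooled estimate is independent of the interaction contrasts, so the chance of a positive pooled test with no flag is a product. For the lost profile at ρ = 0.5 and n = 50 with equal variances, it is 0.926 × (1 − 0.799) = 0.186. Over the structures and sample sizes above it is 3–19%. Over correlations 0.3 to 0.7 it is about 0–34%.

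**Does the reported quantity respond to missing data?** Simulation: 4,000 trials, 55 per arm, ρ = 0.5, true end-of-therapy effect 0.18. In each arm 10% leave after Day 22. In the selective case, vehicle subjects doing worse at Day 22 leave more often (log-odds slope 1 or 2 per SD) and active subjects leave at random. Mean estimates, with ranges over slopes and the two covariance structures:

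| Profile and dropout | Observed-case | MMRM at end of therapy | Pooled MMRM |
|---|---|---|---|
| Building, selective | 0.149–0.164 | 0.179–0.181 | 0.112–0.127 |
| Building, random in both arms | 0.180–0.181 | 0.180–0.181 | 0.113–0.128 |
| Constant, selective (slope 1) | 0.159–0.164 | 0.180 | 0.181 |

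Monte Carlo SE is about 0.001. With a building effect, the pooled value is nearly the same in the first two rows, so it does not show whether dropout has distorted the primary result. When dropout has pulled the observed-case estimate below 0.18, the pooled value lies lower still and points the wrong way. The end-of-therapy contrast recovers 0.18 in all three rows.

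**The case against.** The best case against this is that little depends on it.

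- The MMRM is outside the gate in SAP 7.4.6.5, Protocol 10.3 only says it may be done, and SAP 7.4.4.1 treats p-values as generally descriptive.
- Table 14.2.1.5 shows LS-mean differences by visit beside the pooled p-value, so a reader can see whether the effect changes over time.
- Tables 14.2.1.1 and 14.2.1.2 count subjects with three, two, one or none of Days 41 to 43, so a trivial amount of missing data would be evident.
- One available day is enough to define end of therapy, and Protocol 7.4 asks early discontinuers to complete the Visit 13 evaluations.
- SAP 7.4.4.3 supplies another end-of-therapy difference with CI.
- The 10% in the simulation is the plan's whole allowance for non-evaluable subjects. With 5% dropout the observed-case mean is 0.164–0.173, and with 3% it is 0.169–0.177. The shortfall of 0.003–0.016 is under a quarter of an SE of about 0.07. At 10% it is roughly 0.2 to 0.4 SE.
- The lost-at-end profile has no HDSM-Ax evidence behind it.

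All of this stands, and it limits the consequence. None of it supplies the missing result. The by-visit rows appear to be observed-case ANCOVA, so they share the primary analysis's exposure to dropout. The check in 7.4.4.3 carries earlier values forward, which understates an effect that is still building. The counts show how much is missing but not what it does to the estimate.

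**Conclusion.** The concern holds. As specified, the MMRM output for the continuous primary endpoint does not address the end-of-therapy difference unless the treatment effect is constant over visits.

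For an effect that builds to 0.18, the pooled effect is 55–74% of it in the main cases and 48% in one wider case. It also barely responds to dropout that biases the observed-case estimate. These sizes rest on assumed profiles, correlations and dropout patterns. The reading of the shells does not.

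No gated conclusion changes, and with few subjects missing all of Days 41 to 43 the practical effect would be small. The change should still be made: it makes the sensitivity analysis answer the question it was planned for, at almost no cost.

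**What to change.** In SAP 7.4.4.2, state that the MMRM sensitivity result is the end-of-therapy LS-mean difference for each dose versus vehicle, with CI and one-sided p-value, from the model with treatment-by-visit that is already planned. Add that row to Tables 14.2.1.5 and 14.2.1.6. For consistency, add it to the continuous GSP Tables 14.2.3.9 to 14.2.3.12 as well.

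In the same shells, label the no-interaction p-value as an across-visit summary, and label the by-visit LS-mean and difference rows as ANCOVA.

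The cost is one contrast statement per continuous model and one row plus labels in six shells, with no new data and no new model. SAP section 4 allows minor template changes without documentation in the CSR.
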